6.4.1. Measures

6.4.1. Measures Ws3a

| Participant group | Measures | Time point (month number 1-12) | | | | |
|-------------------|----------------------|--------------------------------|----------|--|--|--|
| Children/yo | - Demographics | Once | 1 | | | |
| ung people | -RMD | Monthly (12) | 1-12 | | | |
| | - Revised Children's | Three times | 1, 6, 12 | | | |
| | Anxiety and | | | | | |
| | Depression Scale | | | | | |
| | (RCADS) | | | | | |
| | - The Bounce | Three times | 1, 6, 12 | | | |
| | Forwards Scale | | | | | |
| | - Sense of | | | | | |
| | Community in | | | | | |
| | Adolescents Scale | Three times | 1, 6, 12 | | | |
| | - Therapeutic | | | | | |
| | Alliance Scale for | | | | | |
| | Children (TASC-r) | Three times | 1, 6, 12 | | | |
| | - SDQ CYP | | | | | |

| | -Pen portrait - Interviews and/or reflective group discussions -Qualtrics written feedback | Twice Fortnightly (24) Three times Three times | 1 & 12 1-12 1, 6, 12 1, 6, 12 | | | | |
|----------------------|--|--|--|--|--|--|--|
| Residential Staff | -Demographics - Professional Quality of Life Scale (ProQOL) - Brief TIC self- assessment | Once Three times Three times | 1 1, 6, 12 1, 6, 12 | | | | |
| | reflective exercise (developed in Ws1) -TiC conversation Tool -Narrative data | Twice Bi-monthly (6) | 1 & 12 2, 4, 6, 8, 10, 12 | | | | |
| Social Workers | -Narrative data (every 8 weeks) | Bi-monthly (6) | 2, 4, 6, 8, 10, 12 | | | | |

Assessments for children and young people

| Instrument used in the | Number of items | Indicative completion |
|-----------------------------|-----------------|-----------------------|
| proposed evaluation | | time |
| Strengths and Difficulties | 25 | 10-15 minutes |
| Questionnaire Self-Report | | |
| version for 11-17 year olds | | |
| (Goodman et al., 1998) | | |
| Revised Children's | 47 | 10-15 minutes |
| Anxiety and Depression | | |
| Scale (RCADS) | | |
| The Bounce Forwards | 34 | 10-15 minutes |
| Scale | | |
| | | |
| Sense of Community in | 36 | 15-20 minutes |
| Adolescents Scale (SOC- | | |
| AS; Chiessi et al., 2010) | | |
| Therapeutic Alliance Scale | 12 | 5-10 minutes |
| for Children (TASC-r; | | |
| Creed& Kendall, 2005) | | |
| | | |

| Instrument used in the | Suitability for the study |
|---|--|
| proposed evaluation | - |
| Strengths and Difficulties Questionnaire (Goodman et al., 1998) | The SDQ is a brief behavioural and emotional screening questionnaire, routinely employed across youth mental health services to collect baseline data, usually at the point of referral. The SDQ captures information about children aged 2–17-year-olds. There is a version for young people aged 11-17-years-old that they can complete on their own, and a parent version and teacher version. Only the parent/carer version and young people's version will be used in the NEST study. Research with children and young people supports the use of the self-report SDQ with young people aged 8-17-years-old and is therefore appropriate to our study. |
| Revised Children's Anxiety and Depression Scale (RCADS) | The Revised Children's Anxiety and Depression Scale (RCADS) is a 47-item self-report questionnaire designed for children and young people aged 8 to 18. It assesses symptoms across six subscales: separation anxiety, social phobia, generalized anxiety, panic disorder, obsessive-compulsive disorder, and major depression. This tool is appropriate for the NEST Study because it helps identify and track anxiety and depression symptoms, which are common in young people who have experienced trauma. By administering the RCADS before, during, and after the intervention, the study can evaluate the effectiveness of trauma-informed care in improving mental health outcomes. Its comprehensive nature and validated use in diverse settings make it a reliable measure for informing and tailoring trauma-informed practices in children's homes. |
| The Bounce Forwards Scale | The Bounce Forwards Scale is a resilience-focused assessment tool designed to measure young people's ability to adapt positively to challenges and adversity. This scale is appropriate for the NEST Study because it aligns with the project's goal of promoting traumainformed care, helping assess how well the intervention enhances resilience and emotional recovery in children who have experienced trauma. By tracking changes in resilience, the scale provides valuable insights into the effectiveness of the traumainformed toolkit being implemented in children's homes. |

Sense of Community in The SOC-AS is a psychological tool designed to measure Adolescents Scale (SOCadolescents' perceived sense of belonging, connection, AS; Chiessi et al., 2010) and support within a specific community, such as their school, neighbourhood, or peer group. This scale evaluates how well adolescents feel integrated and valued within their community, which is particularly important during adolescence—a developmental stage where social connections play a key role in emotional well-being and identity formation. This scale is particularly useful in contexts like residential care settings or schools, where fostering a sense of belonging can significantly improve adolescents' wellbeing and engagement. Therapeutic Alliance The TASC-r is a 12-item self-report measure designed to Scale for Children (TASCassess the quality of the therapeutic relationship from r; Creed& Kendall, 2005) the child's perspective. The scale evaluates both positive and negative aspects of the therapeutic alliance, including goal agreement, task collaboration, and emotional bond. This measure is appropriate for the NEST study as it assesses the quality of the therapeutic relationship, which is crucial in traumainformed care settings like residential homes. The NEST Study focuses on creating nurturing environments for young people who have experienced significant trauma, and building a strong therapeutic alliance is essential to fostering a sense of safety, trust, and empowerment-

Quantitative ssessments for residential staff

1. Professional Quality of Life Scale (ProQOL) - 30 items (5-8 minutes)

Informed Assent/Consent for Interviews

As for other stages of the study, informed assent and/or consent will be obtained prior to the start of the qualitative interviews. Participants will be provided with multiple options to confirm and document their informed consent, depending on whether contact with the research team will be face-to-face or via remote means. These will include: 1) signing a hard copy of the consent form during face-to-face meetings with research workers; 2) returning a signed hard copy of the consent form to the research team via standard mail (using a pre-paid return envelope provided by the research team); 3) returning a signed electronic copy of the consent form to the research team via email, or 4) providing audio-recorded consent (this will be recorded by research workers using an encrypted recording device and stored separately from any research data collected from study participants).

key components of trauma-informed care.

The NEST Study Protocol Version 1.0, 06/12/2024

[figure not shown]
Following consent, the research workers will conduct semi-structured interviews according to the draft topic guides included with this NHS ethics/health research authority (HRA) application. The topic guides used to inform the qualitative interviews will be a living document, updated according to emerging findings from earlier interviews, new published literature in this area and feedback from our ongoing stakeholder consultations.

Interviews may take up to 90 minutes, depending upon how much or little participants wish to say, and will be recorded using encrypted recording devices. Participants will be asked if they would like to receive copies of their interview transcripts and a summary of the emerging findings of the study, for the purposes of ensuring accuracy and contribute to 'member checking' procedures to ensure the trustworthiness of the study findings.

6.6 Keeping in touch calls.

To promote retention in the study, the research workers will contact the link person at each of the homes approximately two weeks before each data collection point and then again a few days prior. These brief telephone calls will be an opportunity for the research workers to remind participants (usually staff) of upcoming research engagement and to resolve pragmatic barriers that may delay or hinder the participant's timely engagement in the follow-ups.

6.7 Safeguarding

Co-investigator [name] is an expert in Child Safeguarding and will advise the team on complex issues or ethical dilemmas that emerge during the study regarding safeguarding. In most instances, Salford's child safeguarding procedures will be followed, in collaboration with the Salford Safeguarding Children Partnership.

7. Definition of end of study

The intervention period is due to end by 31st August 2026, data collection is due to complete by 30th September 2026, and the study will close on 30th April 2027.

| 0 | 1 | 2 | 3 | 4 | 5 | 6 | 7 | 8 | 9 | 10 | 11 | 12 | 13 | 14 | 15 | 16 | 17 | 18 | 19 | 20 | 21 | 22 | 23 | 24 | 25 |
|------------------------------------|--|------|------|------|-----|------|------|------|------|------|-------|-------|-----|------|-------|-------|-------|-------|-------|-----|----|----|----|----|----|
| Pr | Pre-start prep: REC and HRA approvals sought, Research Practitioner appointed. Induct LEAG and | | | | | | | | | | | | | | | | | | | | | | | | |
| | SAB | | | | | | | | | | | | | | | | | | | | | | | | |
| | | | | | | | | | | | | | | | | | | | | | | | | | |
| Workstream 1: Rapid Realist Review | | | | | | | | | | | | | | | | | | | | | | | | | |
| | | | | | | | | | | | | | | | | | | | | | | | | | |
| W | ork | stre | eam | 2: | Exp | ploi | ring | ex | per | ienc | es ar | nd vi | ews | of c | hildr | en a | nd st | takel | nolde | ers | • | • | | | |
| | | | | | | | | | | | | | | | | | | | | | | | | | |
| W | ork | stre | am | 3a | : R | eali | st E | Eval | luat | ion | | | | | | | | | | | | | | | |
| | | | | | | | | | | | | | | | | | | | | | | | | | |
| W | ork | stre | am | 3b | : R | efin | nem | ent | of | Inte | vent | tion | and | Impl | eme | ntati | on T | ooll | cit | | | | | | |
| | | | | | | | | | | | | | | | | | | | | | | | | | |
| D | isse | mir | nati | on a | and | Im | pac | t | | | | | | | • | | | | | | | | | | |
| | | | | | | | | | | | | | | | | | | | | | | | | | |
| PI | PIE | Me | etii | ngs | | | • | | | | | | | | | | | | | | | | | | |
| | | | | | | | | | | | | | | | | | | | | | | | | | |

8. Ethical and regulatory considerations

8.1 Approvals

Before the start of the intervention period, a favourable opinion will be sought from an NHS Research Ethics Committee (REC) for the study protocol, informed assent forms (children aged 15-years-old and younger) consent forms (participants 16-years-old and over) and other relevant study documents. All components of the research involving data collection from research participants will commence following satisfactory NHS Ethics and HRA approval, as well as local Capacity and Capability approval from participating NHS Trusts. The study will be conducted in full conformance with all relevant legal requirements and the principles of the Declaration of Helsinki, Good Clinical Practice (GCP) and the UK Policy Framework for Health and Social Care Research 2017. Where young people are in the care of Salford City Council, depending upon the nature of the care order, consent for a young person's participation will be gained from the placement provider, social worker, or child's named parent/caregiver, as appropriate.

8.2 Regulatory Review & Compliance

Before any site can enrol patients into the study, the CI or designee will ensure that appropriate approvals from participating organisations are in place. Specific arrangements on how to gain approval from participating organisations are in place and comply with the relevant guidance.

For any amendment to the study, the CI or designee, in agreement with the Sponsor, will submit information to the appropriate body (REC, HRA, Sponsor and participating sites) for them to issue approval for the amendment. The CI or designee

will work with sites (R&D departments at NHS sites as well as the study delivery team) so they can put the necessary arrangements in place to implement the amendment to confirm their support for the study as amended.

All correspondence with the REC and HRA will be saved in the Study Master File. The CI or designee will be responsible for the submission of annual reports and safety reports to the REC, the final REC project report / end of study notification and the prompt notification of the premature interruption of the study, should this be warranted.

8.3 Protocol compliance

Thorough training of all research staff at the study onset and subsequent weekly supervision of all research workers (e.g., assistant, therapist, ClinPsyD trainees) throughout their involvement in the study will minimise risk of deviations from protocol. However, accidental deviations from protocol can happen at any time; these will be documented and recorded in a protocol deviations log, which will be saved in the Study Master File. All deviations from protocol will be brought to the attention of the project CI, and promptly communicated to the study Sponsor, so that corrective actions could be promptly implemented. The protocol deviations log will also be reviewed at regular meetings with the experienced research team and professional steering groups for additional scrutiny and suggestions of corrective actions.

8.4 Assessment and management of risk

All digital and face-to-face contact with research participants will be conducted in accordance with bespoke standard operating procedures (SOPs) to manage any risk uncovered as part of the planned research assessments. These will comply with national and local policies for safeguarding children and vulnerable adults. In case our research assessments will uncover significant safeguarding issues or risks, participants' confidentiality may be breached to comply with safeguarding best practice and ensure the safety of all parties. This might involve disclosure of clinical and risk information to the participants' clinical teams and relevant safeguarding teams, as guided by local frameworks and policies for safeguarding children and vulnerable adults. All participants will be informed of the boundaries and limits of confidentiality at the onset of the evaluation.

The study will include the collection and discussion of sensitive topics, and some participants may find these upsetting or potentially distressing. In our experience, severe distress caused by the proposed research procedures will be highly unlikely. Nonetheless, to mitigate risk of distress, all contact with research participants will be conducted according to SOPs to manage assessments in a sensitive and respectful way. We will also follow tried-and-tested protocols for recognising and responding to potential signs of distress during and following contact with research participants. These procedures include, amongst other steps, 1) pausing of any data collection /

interview procedures should a participant become distressed; 2) offering breaks and opportunities for reassurance; 3) reminding participants that their participation is voluntary and of their right to withdraw at any point, without any detriment to them; 4) procedures for signposting participants to appropriate sources of support or summon emergency services in cases of extreme risk to the participant or the public. All participants will be provided with debriefing information that will include the contact details of relevant local support services that participants could access in the event of a crisis. This debriefing document will be updated regularly to ensure that information and resources are as up to date as possible throughout the study.

All research workers contributing to data collection activities will receive regular supervision from a senior researcher within the team as well as access to line management supervision and other ad-hoc supervision and guidance from clinically qualified NHS professionals. All contacts with research participants will take place at pre-specified times agreed by project's CI or individual with delegated responsibility, and according to a 'clinical cover rota' that will guarantee that RAs within the host research centre have prompt access to clinically qualified members of the research team for initial risk management advice.

It is expected that a considerable amount of contact with research participants will be via remote means (e.g., telephone or digital platforms/software approved by the participating NHS organisations, e.g., Microsoft Teams). Risks to the physical safety of the investigator are therefore minimal in these circumstances. Any necessary face-to-face contact will be conducted in full compliance with the lone working policies of the participating NHS Trusts and Higher Education Institutions (HEIs) where the research workers and other research workers will be based, which will include locally adapted safety checking for lone workers SOPs.

8.5 Adverse event reporting and harms

Throughout the participants' involvement in the study, best practice, professional guidelines, and local NHS policies for monitoring mental state and risk for participants will be followed and will be facilitated by close liaison with clinical teams. Any adverse event (AE), clinically significant deterioration in the participants' mental state or change in risk information will be promptly communicated to responsible clinicians to ensure appropriate monitoring and provision of support.

Any AE observed over the course of the research will be documented and reported according to bespoke SOPs that will fully comply with appropriate HRA safety reporting procedures for non-CTIMP studies, Sponsor's requirements, and local R&D policies of participating NHS organisations. For example, all research contacts will be recorded in clinical notes and signed consent forms will also be uploaded/attached to clinical notes.

The occurrence of AEs will be monitored and systematically recorded by study staff. Research workers may become aware of an AE in a variety of ways, including

The NEST Study Protocol Version 1.0, 06/12/2024

participants' prompted or unprompted disclosure, information received from responsible clinicians, information extracted through clinical notes and usual monitoring of the participants' mental health and welfare as part of therapy sessions delivered as part of the trial. To ensure active surveillance of harms, at each follow-up assessment, the research workers will actively check for the occurrence of specific AEs using a structured checklist completed with the participant.

AEs are defined in line with standard HRA guidance as any untoward medical occurrence, unintended disease or injury, or untoward clinical signs in participants, whether or not related to the treatment, which require additional support or input from health professionals. Any clinically significant increase in presenting difficulties reported by participants (i.e., operationalised as an unresolved exacerbation in distress/mental health symptoms requiring increased involvement from the care team, e.g., a change in treatment plan) and reports of distress or complaints associated with therapy or other study procedure would also constitute AEs.

AE forms will be sent to the project CI (or another clinically qualified person with delegated responsibility) and assessed for:

- Severity (i.e., classified as mild, moderate, and severe according to the impact of the event on the person at the time, irrespective of whether the event also meet 'seriousness' criteria).
- Relatedness (i.e., whether the event resulted from administration of any of the research or therapy procedures, according to available information, e.g. temporal proximity to a study procedure; according to the report of the participant and the opinion of the clinical team).
- Expectedness (rated only in cases where the event is judged as related to the study procedures and intervention, and pertaining to whether the nature and severity of the observed reaction appears inconsistent with those expected from the study procedures.
- Seriousness (i.e., whether the outcome of the event meet criteria for a SAEs, including death and life-threatening events, incidents which acutely jeopardise the health or psychological well-being of the individual, events resulting in immediate hospital admission and/or persistent or significant disability or incapacity, and events resulting in injury requiring immediate medical attention, including A&E visits for mental health reasons).

Only SAEs judged to be unexpected and related to the study will be reported to the REC as per standard HRA procedures, within 15 days of the CI first becoming aware of the event. This means the REC will be notified based on the initial report, even if the final report is pending. All reportable SAEs will be reported to the Sponsor in accordance with timelines and procedures mandated by Sponsor-specific guidelines and SOPs.

All completed AE forms will be stored locally in site master files, and a central AE log will be maintained as per HRA guidance to ensure effective safety monitoring. Throughout the trial, AEs and SAEs will be regularly audited at monthly team

The NEST Study Protocol Version 1.0, 06/12/2024

meetings to monitor trends in AE/SAE and their implications for the ongoing delivery of the study procedures. The Sponsor and Funder will immediately be notified on receipt of any information that raises material concerns about safety of the study procedures and interventions.

Any required urgent safety measures (i.e. steps taken by the CI and/or research team in the event that there is an immediate risk to a participant or participants, without the prior approval of the NHS REC/HRA) will be notified by the CI must to the REC immediately by telephone and then follow-up with a substantial amendment within 3 days outlining the measures that have been taken and its rationale. A copy of the amendment will be submitted to the Sponsor for expedite review and sponsor authorisation of the amendment before being submitted to the NHS REC/HRA.

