Finally, we will draw upon the realist programme theory of the intersections between TIC, adversity, resilience, and residential care with the findings from the EBCD process to develop the new TIC intervention and implementation toolkit for WP3. We will hold two half day events with the LEAG and SAB, as described in WP1, to gather feedback on the drafted new TIC intervention and implementation toolkit and make final amendments. Together, the perspectives offered through the interpretation of data presented to these groups will provide opportunities for metalearning on the process, factors for decision making, and insights into how the intervention might operate within the children's home environment.

The residential nature of the homes and enthusiasm from the partner will ensure there are no delays with recruitment as all parties are already on-site. Additionally, if we need to extend this part of the research process, we can do, with little impact on WP3 as all activities are being undertaken in the same locations.

WS2 Output: A new TIC intervention with an implementation toolkit tailored for the unique context of children's homes, piloted and evaluated in WP3.

4. Pilot and Evaluation

Workstream 3a: Realist Evaluation

WP3a aims to test and refine the programme theory from WP1 and our new TIC intervention and implementation toolkit across the homes, evaluated using realist evaluation (Flynn et al, 2019, Pawson and Tilley, 1997). Our hypothesis is that the intervention will bring about observable change in terms of creating a culture of resilience, community cohesion and community spirit, as well as enhancing individual wellbeing, attainment, and resilience in the face of stressors, transitions, and adversity. We envision WP1 and WP2 will inform:

- Key performance indicators, identified and developed through WP1 and 2, and will help set clear SMART goals for the home managers and staff.
- A theoretical induction in resilience, recovery, adversity, and TIC specifically in relation to children in care, taught to staff at all levels through three training days, team formulation sessions and ongoing supervision, supported by SP, EF, and the RP.

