- The TIC intervention will be taught to staff, who will be supported in implementation through training, supervision, and support workshops. This process will also help the research team build the implementation toolkit around the intervention as it is used, collecting stories from practice, reflective case examples, and problem/solution-based learning examples.
- An integrity checklist, implemented through peer observation and support from the research team.
- An embedded schema for team formulation meetings and supervision for the frontline staff that will initially be run by members of the research team, learnt by the home staff, and then adopted so it can be continued after the pilot has finished.
- SP and EF are experienced trainers and consultants within children's homes, and will conduct the training, supervision, and team formulation sessions, supported by the RP and, in time, home managers.

Data collection will include:

IRAS ID: 337194 NIHR206567

- Personal demographics of all participants at the start of the study or when a new member of staff or young person joins each home.
- Tabulated data from the monthly routine monitoring data (RMD), which all children's homes routinely collect in relation to child development, educational attainment, incidents of concern, and their wellbeing.
- A TIC conversation tool of 10 implementation domains from Scotland's
 Trauma-informed practice toolkit, conducted with house managers and senior
 staff at the start and end of the study.
- Quantitative data to track children's development and wellbeing at the start, middle and end of the pilot:
- 1. RCADS Self-Reported (8-18 years old)
- 2. RCADS Parent version
- 3. Therapeutic Alliance Scale for Children, Revised (TASC-R)
- 4. Trauma-Informed Care Pen Portrait Template
- 5. Resilience Scale for Care Experienced Young People
- 6. Sense of Community in Adolescents Scale (Chiessi, Cicognani & Sonn, 2010)
- The strengths and difficulties questionnaire (SDQ) will be given to children and their key workers at the beginning and end of the pilot, or when the child leaves the home if before the end of the pilot. This plan has been discussed with stakeholders and appears acceptable.
- Key workers and home managers will keep a fortnightly pen portrait documenting intervention integration, integrity, and implementation, which will be accompanied by supportive Microsoft Teams and in-person supervision with a member of the research team.

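### Section 8.5 defines adverse-event relatedness by research and therapy procedures, but the study delivers no therapy, so the definition as written omits the trauma-informed care intervention

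*Protocol*

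**What the plan says.** Protocol Section 8.5 uses the word therapy three times.

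- Among the ways in which staff may learn of an adverse event (AE), it lists monitoring of participants' "mental health and welfare as part of therapy sessions delivered as part of the trial".
- It counts as AEs "reports of distress or complaints associated with therapy or other study procedure".
- It defines relatedness as "whether the event resulted from administration of any of the research or therapy procedures".

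The same section then uses the relatedness judgement twice. Expectedness is "rated only in cases where the event is judged as related to the study procedures and intervention". For the REC, "Only SAEs judged to be unexpected and related to the study will be reported to the REC", with a limit of 15 days from the CI first becoming aware of the event.

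Section 4 (Workstream 3a) describes what is delivered. The theoretical induction is "taught to staff at all levels through three training days, team formulation sessions and ongoing supervision". For the intervention itself: "The TIC intervention will be taught to staff, who will be supported in implementation through training, supervision, and support workshops". The research team first runs team formulation meetings and supervision for frontline staff, and the homes then take these over. Children receive the intervention through the care that these staff give.

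**The concern.** The therapy wording has no counterpart in the study, and it appears in the one sentence that tells the assessor how to decide relatedness. That decision controls two later steps: whether expectedness is rated, and whether a serious adverse event (SAE) goes to the REC within 15 days.

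The most plausible route by which this intervention could harm a child is a change in daily care after staff have been trained. Such a change is neither a research procedure nor therapy, so the definition does not plainly cover it. The pilot also has no comparison group, so harm cannot be judged by setting arms side by side. The individual rating carries more of the causal judgement than it would in a controlled trial.

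**Working it through.** There is no figure to reproduce and no arithmetic to do. The check compares the sentences of Section 8.5 with one another, and then with the rest of the protocol.

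**Step 1: scope of each statement in Section 8.5.**

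| Statement | What it does | Scope | Intervention named? |
|---|---|---|---|
| Source list | Says how AEs come to light | Includes therapy sessions | No |
| AE definition | Adds distress and complaints | Therapy or another study procedure | No |
| Relatedness bullet | Defines relatedness | Research and therapy procedures | No |
| Expectedness bullet, condition | Says when expectedness is rated | Study procedures and intervention | Yes |
| Expectedness bullet, reference | Says what the reaction is compared with | Study procedures only | No |
| REC sentence | Selects SAEs for the 15-day report | The study as a whole | Not by name, but wide enough |
| Closing sentence on Sponsor and Funder | Triggers immediate notification | Study procedures and interventions | Yes |

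Two rows list procedures and intervention as separate things. The protocol's own usage therefore does not let one assume that research procedures include the intervention.

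**Step 2: is there any therapy in the study?** Section 1 says that the toolkit covers staff training, supervision, trauma-aware care and governance. Section 4 adds team formulation, support workshops and an integrity checklist. Neither mentions therapy sessions. Outside 8.5, the idea appears in Section 8.3, which gives a therapist as an example of a research worker, and in Section 8.6, which refers to recordings of therapy sessions. The therapeutic alliance questionnaire in Section 6.4.1 is an outcome measure and implies no sessions. Workstreams 1 and 2 will still shape the intervention, but nothing in the plan foresees therapy.

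**Step 3: follow one event through the rules.** Suppose that key workers, after training, change how they respond to distress, and a child then attends A&E for mental health reasons. Section 8.5 lists such a visit as serious.

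1. Relatedness bullet, read literally: the event came from no research procedure, and there is no therapy. The literal answer is unrelated.
2. Expectedness is rated only for related events, so it is not rated.
3. The REC report requires an event that is both unexpected and related, so no 15-day report is made.

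If the definition named the intervention, the assessor could rate the event related at step 1 and go on to step 2. There the reference would still be wrong, because expectedness is judged against study procedures alone. That second flaw would tend towards more reporting rather than less, but it gives the assessor the wrong yardstick.

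**The case against.** The strongest reply is that therapy is simply a carried-over label for the intervention. The next bullet speaks of procedures and intervention together, and the AE definition uses treatment for the same thing. The assessor is the CI or a clinically qualified delegate, who also weighs the participant's report and the clinical team's opinion. A sensible assessor may well read the word that way, and nothing in the protocol shows anyone reading it otherwise. This limits the likely effect. It does not remove the defect, because the rule that decides REC reporting should not depend on the assessor replacing a wrong word.

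A reader might infer three stronger points, and the protocol supports none of them.

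- *That 8.5 contains three competing relatedness tests.* It contains one definition and two sentences that apply it. One assessor makes one rating. What can fairly be said is that the three statements differ in scope.
- *That harm from the intervention would go unreviewed.* The oversight committee's remit covers patient safety issues including any SAE. AEs and SAEs are audited at monthly team meetings. The Sponsor and Funder are told at once of information that raises material concerns about the intervention's safety. None of these waits for a related rating. What could be missed is the 15-day REC report.
- *That routine monitoring data, pen portraits and questionnaire scores are wrongly left out as AE sources.* The source list is expressly open, and at follow-ups research workers will "actively check for the occurrence of specific AEs using a structured checklist completed with the participant". Details are left to operating procedures that are not shown. Routine data may include anonymous returns for children who did not opt in, and Section 4 describes the fortnightly portraits as records of implementation. New surveillance may be worth discussing, but it does not follow from this wording fault.

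**Conclusion.** The point holds as a wording defect in safety reporting. The single definition of relatedness does not name the intervention under test, other sentences in the same section do or are broader, and the therapy that it names is not part of the study. The consequence is that an SAE caused by changed daily care could be rated unrelated and not sent to the REC within 15 days.

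Its size is three uses of therapy and one mismatched expectedness reference in 8.5, and one sentence in 8.6. The number of events that might be misrated cannot be derived without an event rate. No analysis, sample size or error rate is affected.

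The conclusion rests on two assumptions: that the co-produced intervention will contain no therapy sessions, as the present plan indicates, and that the unseen operating procedures do not already redefine relatedness. If they do, the protocol should still say the same.

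**What to change.** In Section 8.5:

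1. Define relatedness as *whether the event resulted from any research procedure or from the TIC intervention, including resulting changes in day-to-day care*.
2. Use the same phrase in the condition for rating expectedness, in the reference against which expectedness is judged, and in the REC sentence.
3. In the AE definition, replace the reference to therapy with the TIC intervention.
4. Delete therapy sessions from the list of AE sources.

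In Section 8.6, delete the sentence on recordings of therapy sessions, or say which recordings it means.

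This costs an amendment of a few sentences and needs no new data collection. The one real downside is that an intervention acting on all daily care is hard to rule out as a cause, so somewhat more events may be rated related. For children in residential care, that is an acceptable price for an unambiguous rule.
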